##### Day 0 = day of index procedure (TAVI or SAVR):

- 30 days (- 7 days and + 14 days)
- 3 months (90 ± 14 days)
- 6 months (180 ± 30 days)
- 12 months (365 ± 30 days)
- 18 months (545 ± 60 days)
- 24 months (730 ± 60 days)
- 3 years (1080 ± 60 days)
- 4 years (1440 ± 60 days)
- 5 years (1800 ± 60 days)

All randomized subjects will complete long-term follow-up through at least 5 years. Based on clinical assessments or regulatory requirements, follow-up may be extended to up to 10 years post-index procedure. Upon completion of the final protocol visit (discontinuation) subject participation will be considered complete and the patient should then be followed per the local standard of care for their condition.

Note: For subjects where the Index Procedure is never attempted (eg. subject withdraws consent for the procedure but agrees to complete follow-up) follow-up intervals will be calculated from the 31st days post-randomization (i.e. the 1st day after the 30 day window from randomization to complete the Index Procedure).

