#### *C.4.19 Subject Withdrawal or Discontinuation*

All subjects will be encouraged to remain in the trial through the last follow-up visit at month 60. Subjects who discontinue participation prematurely after randomization will be included in the analysis of results (as appropriate) but they will not be replaced in the enrollment of total trial subjects. If a trial subject is discontinued from the trial early, the reason for discontinuation should be documented in the patient file and a Study Exit eCRF must be completed. If discontinuation is because of safety concerns or lack of effectiveness, the subject shall be asked to be followed for collection of ongoing safety data outside the clinical investigation.

The trial site and Sponsor will make every effort to have all subjects complete the follow up visit schedule. A subject will not be considered lost-to-follow-up unless all efforts to obtain compliance are unsuccessful. At a minimum, the effort to obtain follow-up information must include three attempts to make contact via telephone and if contact via phone is not successful, a traceable letter from the Investigator must be sent to the subject's last known address. Should both telephone and mail efforts to contact the subject be unsuccessful, the subject's primary physician should be contacted. Subjects will then be deemed lost to follow up. All contact efforts to obtain follow-up must be documented in both the subject's medical records and in the trial eCRFs.

If a subject officially withdraws from the trial but is willing to allow either regular vital status determinations for the trial or a one-time vital status determination, these are to be conducted per the follow-up visit schedule or only at the last planned follow-up visit, respectively, and may be conducted via telephone.

If a subject discontinues the trial at any time, is withdrawn from the trial early, or completes all protocol required follow-up they should then be followed per the local standard of care for their condition.

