### C.6.5 Primary Analysis

The primary endpoint of all-cause mortality or disabling stroke at 24 months will be evaluated using the absolute difference of the TAVI rate and the SAVR rate for all-cause mortality or disabling stroke during a fixed follow-up of 24 months' time. The hypothesis test is designed to show non-inferiority of TAVI to SAVR for the primary endpoint.

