#### *C.6.6 Missing Data and Planned Sensitivity Analyses (Primary Objective)*

Every effort will be undertaken to minimize missing data. However, some missing data is inevitable, and the trial is designed with the expectation that there may be up to 6% of primary data missing at 24 months. The reasons for missing data will be described in detail and evaluated for assessment of possible bias. The distribution of prognostic factors between patients with data and those without data will be examined to evaluate any potential sources of bias.

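### The one-time vital-status check for withdrawn subjects is set at month 60, about three years after the 24-month primary endpoint, so nearly all such checks come too late for the final primary analysis

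*Combined protocol and SAP*

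**What the plan says.** Protocol C.4.19 offers two arrangements to a subject who officially withdraws but still allows vital status to be followed: regular checks, or "a one-time vital status determination, these are to be conducted per the follow-up visit schedule or only at the last planned follow-up visit, respectively". The closing word ties regular checks to the visit schedule and the single check to the last visit. The section also identifies that visit, because subjects are encouraged to "remain in the trial through the last follow-up visit at month 60". C.4.9 sets the 24-month visit at day 730 ± 60 and the 5-year visit at day 1800 ± 60, and allows follow-up to be extended to 10 years.

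Under C.6.5 the primary endpoint of "all-cause mortality or disabling stroke at 24 months will be evaluated using the absolute difference" between the TAVI and SAVR rates. C.6.5.2 places the final analysis when all mITT subjects have been followed to 24 months, with an interim look for an early win when 1400 mITT subjects have reached 12 months. C.6.6 accepts that "there may be up to 6% of primary data missing at 24 months".

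**The concern.** Death is the larger part of the primary endpoint: about 15 of the assumed 17 percentage points in the sample size justification. It can be ascertained by telephone, which C.4.19 expressly allows. For a subject who permits exactly one contact, the rule spends that contact on 5-year status and leaves 24-month status unknown when the primary comparison is made. A site that called earlier on its own initiative would be departing from the protocol.

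Nothing else in the text reviewed fills the gap. C.4.15 asks for vital status when a visit is missed, but it is written for subjects still in the trial. The telephone, letter and primary-physician steps in C.4.19 concern loss to follow-up. C.6.6 describes missing data and compares prognostic factors, but recovers no outcomes. Assignment is open-label (C.4.5), so withdrawal after the procedure could depend on arm and health. A dated death learned of at month 60 would settle 24-month status, but only after the primary decision and, if non-inferiority is declared at the interim look, after the regulatory submission.

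**Working it through.** **Inputs.** Visit days: C.4.9. Accrual of about 36 months: C.3.5. Analysis timing, 1600 mITT subjects, 1:1 allocation, 7-point margin, 17% event rate, 15% mortality and 6% dropout: C.6.5.1 and C.6.5.2. Missing-data allowance of 6%: C.6.6.

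**1. The plan's own figures.** The Farrington-Manning formula with 17% in both arms, margin 0.07, one-sided alpha 0.05 and 95% power gives 628.6, so 629 per arm and 1258 in total, as stated. Then 1258 / 0.94 = 1338.3, rounded up to 1339, also as stated. The 6% is therefore a genuine planning input.

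**2. Gap between endpoint and check.**
- Nominal: 60 − 24 = 36 months.
- By visit day: 1800 − 730 = 1070 days, or 1070 / 365.25 = 2.93 years.
- Across the windows: 1740 − 790 = 950 days (2.60 years) to 1860 − 670 = 1190 days (3.26 years).

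**3. Share of one-time checks done before the final cut.** Assume uniform accrual over 36 months and a cut when the last subject reaches 24 months, at calendar month 36 + 24 = 60. The share is (60 − check time in months) / 36.
- Check at a nominal 60 months: 0%.
- Day 1800 (1800 / 30.4375 = 59.14 months): 0.86 / 36 = 2%.
- Day 1740 (57.17 months): 2.83 / 36 = 8%.

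So 92% to 100% fall after the cut. With a 6-month lag to the cut (assumption), 17% to 25% would be in time. With 48-month accrual (assumption), 25% to 43% would be, depending on lag and visit day.

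**4. Interim look.** Under the same accrual it falls at 1400 / 1600 × 36 + 12 = 43.5 months. No subject can have reached even day 1740 by then, so no one-time check informs it.

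**5. Deaths at stake, upper end.** The whole missing-data allowance is 0.06 × 1600 = 96 subjects.
- Full 15% mortality applied to all 96: 96 × 0.15 = 14.4 deaths. This is a ceiling, because a subject must be alive to withdraw.
- Withdrawals uniform over 24 months with constant hazard (assumption): the cumulative hazard is −ln(0.85) = 0.1625, and mean residual mortality is 1 − 0.15 / 0.1625 = 7.7%. That gives 96 × 0.077 = 7.4 deaths.

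**6. If only part of the 96 are one-time consenters (assumption).**
- 10% (9.6 subjects): 0.7 deaths at 7.7%, 1.4 at 15%.
- 50% (48 subjects): 3.7 deaths at 7.7%, 7.2 at 15%.

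The range is about 1 to 7 deaths.

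**7. Scale against the margin.** With all 96 affected and every one of those deaths in a single 800-subject arm, 14.4 / 800 = 1.8 points and 7.4 / 800 = 0.9 points, against 7. An even split would largely cancel in the difference.

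**The case against.** The strongest reply is that this is a deliberate trade-off of small reach. Regular checks are the first option, and they cover 24 months. Only subjects who decline them and accept exactly one contact are affected, and no document sizes that group. The 6% allowance also includes loss to follow-up and refusal of all contact. Secondary endpoints run to 5 years, so a month-60 call has a purpose. The primary population is mITT, so subjects who leave on learning their assignment, before any procedure, are not in it; that removes the most obvious route to arm-dependent withdrawal. The consent templates and the detailed SAP text were not in the material reviewed, so permission for record searches, or a model for missing outcomes, cannot be ruled out.

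Most of this stands, and it limits the size. It does not rescue the timing: the single contact serves a secondary purpose at the expense of the primary endpoint, and a modelled outcome is no substitute for a death that could have been observed.

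Three stronger readings are tempting but unsupported.
- A reader might infer that subjects who discontinue for safety or lack of effectiveness leave the endpoint, because "the subject shall be asked to be followed for collection of ongoing safety data outside the clinical investigation". C.4.19 does not say so. It keeps discontinued subjects in the analysis as appropriate, and the vital-status options are open to anyone who officially withdraws.
- A reader might take 14 deaths as the expected loss. That treats every missing subject as a one-time consenter and applies full 24-month mortality to people alive at withdrawal.
- A reader might expect the same call to recover disabling strokes. Section O.2 defines these by the modified Rankin score at 90 days against the pre-stroke baseline, and C.4.11 assigns that scoring to a neurologist or stroke specialist. A late vital-status call cannot establish it.

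**Conclusion.** The point holds as a timing flaw of modest size. As written, C.4.19 places the one-time check about three years after the primary endpoint. Under the planned 36-month accrual nearly all such checks fall after the final primary analysis. They are not strictly all too late: some early enrollees could be reached in time, and more if accrual or the data cut ran late.

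The number of deaths affected is bounded rather than known: about 7 if all 96 subjects are one-time consenters with evenly spread withdrawal and constant hazard, about 14 as a ceiling, and about 1 to 7 if 10% to 50% are. These shares are assumptions. The effect would rarely decide a comparison with a 7-point margin, and the documents do not support a claim that it biases the result in a particular direction. The reason to act is that the loss is avoidable at almost no cost.

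**What to change.** In C.4.19 and the matching consent line, set the one-time determination on or after day 730 and before the database lock for the primary analysis, and record the date of any death. Where the subject agrees, offer a second contact at month 60. A subject who withdraws with 24-month status already known can keep the single check at month 60.

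The cost is one protocol sentence and one consent line; the same telephone call is made earlier. The downside is that a subject who allows only one contact will have no 5-year vital status. Sample size and analysis method do not change.

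The change helps the final analysis. It helps the interim look only for subjects already past 24 months: with uniform accrual and a look at month 43.5, those enrolled in the first 43.5 − 24 = 19.5 months, or 19.5 / 36 = 54% of the planned accrual.

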#### *C.4.20 Termination or Discontinuation of Trial*

Medtronic may decide to suspend or prematurely terminate the trial. If the trial is terminated prematurely or suspended, Medtronic shall promptly inform the clinical investigators of the termination or suspension and the reason(s) for this. The investigator shall then promptly inform the reviewing MEC/IRB.

Possible reasons for early trial termination include:

- Unanticipated Adverse Device Effect (UADE) or Unanticipated Serious Adverse Device Effect (USADE) presents an unreasonable risk to patients
- Recommendation from DSMB (eg. significant safety concerns, statistical futility)

If the trial is terminated early, the Sponsor will, as soon as possible, provide a written statement to the Investigators to enable prompt notification of the IRB/MECs. The Sponsor will also inform the FDA. If the trial enrollment is terminated early, the follow-up visits will continue for all enrolled subjects.

## C.5 Adverse Events

### C.5.1 Definitions

The definitions presented in this section allow for a clear understanding of adverse event data collection and subsequent analysis.

#### C.5.1.1 Adverse Event

An adverse event (AE) is any untoward medical occurrence, unintended disease or injury, or untoward clinical signs (including abnormal laboratory findings) in subjects, users or other persons, whether or not related to the investigational medical device.

NOTE 1: This definition includes events related to the investigational medical device or the comparator.

NOTE 2: This definition includes events related to the procedures involved.

NOTE 3: For users or other persons, this definition is restricted to events related to investigational medical devices.

The following events in **Table 4** are expected to occur with any surgical implant and therefore should not be reported as AEs, unless they occur outside of the stated timeframe:

**Table 4: Expected Events**

Description of the Event	Timeframe (hours) from Procedure
Anesthesia-related nausea and/or vomiting	24
Low-grade fever (<100°F or <37.8°C)	48
Back pain related to laying on the procedure table	72
Incisional pain (pain at access site)	72
Sleep problems or insomnia	72
Mild to moderate bruising or ecchymosis	168

#### C.5.1.2 Serious Adverse Event

A serious adverse event (SAE) is an event that:

- Led to death
- Led to serious deterioration in the health of the subject, that either resulted in:
  - a life threatening illness or injury, or
  - a permanent impairment of a body structure or a body function, or
  - inpatient or prolonged hospitalization, or
  - medical or surgical intervention to prevent life-threatening illness or injury or permanent impairment to a body structure of a body function
- Led to fetal distress, fetal death or a congenital anomaly or birth defect

NOTE: Planned hospitalization for a pre-existing condition, or a procedure required by the CIP, without serious deterioration in health, is not considered a serious adverse event.

In addition to above standard definition of SAE, the following events will also be defined as serious in the SURTAVI Trial, including events that do not meet the above criteria for SAE.

- Stage 2 and 3 acute renal injuries
- Life-threatening and Major bleeding events
- Any new or worsening LBBB or RBBB that requires the placement of a permanent pacemaker and/or surgical or invasive intervention
- All myocardial infarctions
- Disabling strokes
- Major vascular complications

Events that do not meet these criteria are considered non-serious.

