#### C.5.2.1 Serious Adverse Events (SAEs)

The Investigator shall notify the sponsor immediately but not later than within 3 calendar days of first learning of any SAE using the EDC system [MEDDEV 2.7/3]. If necessary, the Investigator may be requested to provide copies of source documentation regarding the event (eg., physician/nurse notes or summaries). The Investigator should also notify their IRB/MEC and, if applicable, local regulatory agencies, per their requirements.

Medtronic will conduct an evaluation of the event and if it is determined by Medtronic to be a UADE or USADE, it will be reported as described in the following sections.

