#### *C.5.4 Data Safety Monitoring Board (DSMB)*

An independent, unblinded DSMB will be established and will be comprised of at least 3 experts, including a chairperson. The DSMB will have a minimum of one cardiac surgeon, one interventional cardiologist and one statistician, and will be independent of Medtronic and the trial

investigators. Investigators participating in the trial may participate in the meetings to offer clarification surrounding events, but will not have voting privileges. Medtronic personnel may facilitate the DSMB meeting but will not have voting privileges. The DSMB will meet (via teleconference or in person) prior to the first subject enrollment to establish procedures for DSMB review, chairman appointment and guidelines for trial recommendations. The full DSMB will meet on a periodic basis to perform a comprehensive data review and will meet more frequently when needed. Primary and safety-related secondary endpoints may also be reviewed at these meetings. Meetings will consist of both open and closed sessions.

The DSMB will also perform a supplemental review of, at a minimum, all serious adverse events and deaths and any other data requested by the DSMB on a more frequent periodic basis to ensure patient safety. DSMB members will review the report, and when necessary provide recommendations about the conduct of the trial and/or request a full DSMB meeting.

A DSMB charter will be developed and approved by Medtronic and the DSMB members. The committee will outline the criteria for both the full DSMB meeting and supplemental DSMB reviews within the DSMB charter.

Following each full DSMB meeting, the board will report to Medtronic in writing and may recommend changes in the conduct of the trial. These DSMB recommendations may include recommendations on trial status such as continuing the trial without modifications, continuing the trial with modifications, stopping the enrollment in the trial or a specific trial arm, or recommendations about trial conduct including recommendations around enrollment or protocol deviations.

In the case of UADEs or USADEs, if Medtronic and the DSMB determine that the event presents an unreasonable risk to the participating subjects, Medtronic must terminate the clinical trial within 5 working days after making that determination and not later than 15 working days after Medtronic first receives notice of the effect. [21 CFR 812.46]. All clinical sites will be notified of this action.

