### STROKE and TIA

Stroke and TIA will be defined according to the Valve Academic Research Consortium (VARC)-2; Updated Standardized Endpoint Definitions for Transcatheter Aortic Valve Implantation (TAVI); 2012-10-09 and the FDA's Current Thinking Regarding Neurological Assessments for Transcatheter Valve Trials (July 25, 2011).

Diagnostic Criteria

 
• Acute episode of a focal or global neurological deficit with at least one of the following: change in level of consciousness, hemiplegia, hemiparesis, numbness or sensory loss affecting one side of the body, dysphasia or aphasia, hemianopia, amaurosis fugax, or other neurological signs or symptoms consistent with stroke
 
• Stroke: duration of a focal or global neurological deficit <math>\geq</math> 24 hours; OR < 24 hours available neuroimaging documents a new hemorrhage or infarct; OR the neurologic deficit results in death
 
• TIA: duration of a focal or global neurological deficit <24 hours, any variable neuroimaging does not demonstrate a new hemorrhage or infarct
 
• No other readily identifiable non-stroke cause for the clinical presentations (eg. brain tumor, trauma, infection, hypoglycemia, peripheral lesion, pharmacological influences) to be determined by or in conjunction with designated neurologist*
 
• Confirmation of the diagnosis by at least one of the following:               
 
○ Neurology or neurosurgical specialist
 
○ Neuroimaging procedure (CT scan or brain MRI), but stroke be diagnosed on clinical grounds alone
 
 
 

Stroke Classification

 
• Ischemic: an acute episode of focal cerebral, spinal or retinal dysfunctions caused by infarction of the central nervous system tissue
 
• Hemorrhagic: an acute episode of focal cerebral, spinal or spinal dysfunctions caused by intraparenchymal, intraventricular, or subarachnoid hemorrhage
 

Stroke Definitions

 
• Disabling stroke: an mRS score of 2 or more at 90 days and an increase in at least one mRS category from an individual's pre-stroke baseline
 
• Non-disabling stroke: an mRS score of < 2 at 90 days or one that does not result in an increase in at least one mRS category from an individual's pre-stroke baseline
 

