\* Patients with non-focal global encephalopathy will not be reported as a stroke without unequivocal evidence based upon neuroimaging studies

+ Modified Rankin score assessments should be made by qualified individuals according to certification process.

Clinically important disabilities (disabling strokes) will be considered to be serious adverse events.

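### The default SAE rule for stroke cannot be applied until the 90-day mRS, so a stroke meeting no standard criterion may be notified later and be missing from the DSMB's guaranteed SAE review for about 90 days

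*Combined protocol and SAP*

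**What the plan says.** Section C.5.1.2 first gives the standard SAE criteria: death, life-threatening illness, permanent impairment, hospitalization ("inpatient or prolonged hospitalization, or"), or intervention to prevent such outcomes. It then adds a trial-specific list under the words "the following events will also be defined as serious in the SURTAVI Trial, including events that do not meet the above criteria for SAE". Myocardial infarction is on that list without restriction. Stroke is there only as "Disabling strokes". The section closes by treating anything outside these criteria as non-serious.

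The Stroke and TIA entry in O.2 defines the qualifying term: "Disabling stroke: an mRS score of 2 or more at 90 days and an increase in at least one mRS category", measured against the subject's own pre-stroke baseline. The same entry repeats the restriction: "Clinically important disabilities (disabling strokes) will be considered to be serious adverse events".

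Three other provisions determine what follows from this classification:

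- C.5.2.1 sets the SAE deadline: "The Investigator shall notify the sponsor immediately but not later than within 3 calendar days of first learning of any SAE using the EDC system".
- C.5.2.5 allows 15 calendar days from first learning for every other adverse event.
- C.5.4 describes a review held more often than the full DSMB meetings: "The DSMB will also perform a supplemental review of, at a minimum, all serious adverse events and deaths", together with other data that the DSMB asks for.

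**The concern.** The added list is a safety net. It serves only events that the standard criteria miss. A net of that kind has to be usable when the site fills in the report, and the stroke entry is not, because membership depends on a score taken 90 days later. Acute kidney injury, by contrast, is staged in O.2 from changes up to 7 days after the procedure.

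The gap is most likely to matter for deficits found in hospital. Both arms have an NIHSS within 24 hours of the procedure and a full neurological examination at discharge. A mild deficit found then concerns someone who is already an inpatient, so the hospitalization criterion is met only if the stay is judged to be prolonged. Whether the impairment is permanent may not yet be known.

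Disabling stroke is a component of the primary endpoint, and treatment assignment is open. Whether such an event enters the guaranteed safety listing promptly should not depend on how each site interprets an entry that it cannot yet apply. SAE status also triggers steps in C.5.2.1 that C.5.2.5 does not attach to other adverse events: the sponsor's evaluation for an unanticipated device effect, and the investigator's notice to the ethics committee.

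**Working it through.** The plan states no figure to reproduce. The check is date arithmetic on the protocol's own deadlines.

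**Inputs**

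- SAE notice: 3 calendar days from first learning (C.5.2.1).
- Notice of any other adverse event: 15 calendar days from first learning (C.5.2.5).
- Disabling status: mRS at 90 days (O.2, Stroke and TIA).
- mRS after a neurological event: at 7 days or discharge, at 30 days and at 3 months (C.4.11). No rule says how to class a stroke from the earlier scores.
- Assumptions: the site learns of the stroke on the day of onset (day 0), and the 3-month mRS is done on day 90.

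**Step 1: which strokes are affected.** A stroke that meets a standard criterion is an SAE at once and the list is not needed. The list matters only for a stroke that meets none. For that stroke the entry cannot be decided at day 0, and the closing sentence of C.5.1.2 makes it non-serious in the meantime.

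**Step 2: notice to the sponsor.**

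- As written: day 0 + 15 = day 15.
- If all strokes were serious by default: day 0 + 3 = day 3.
- Largest difference: 15 − 3 = 12 days.

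**Step 3: entry into the DSMB's guaranteed SAE listing, for a stroke that proves disabling.**

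- As written, through the list alone: day 90 + 3 = day 93.
- If all strokes were serious by default: day 0 + 3 = day 3.
- Difference: 93 − 3 = 90 days.

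Day 93 is the latest date under these assumptions. If a standard criterion is met earlier, for example through a later admission or a finding at the 30-day assessment, the event becomes an SAE at that point. The interval between supplemental DSMB reviews is not stated, so these dates show when an event becomes eligible for the listing, not when the DSMB reads it.

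**The case against.** The strongest reply is that little escapes the protocol's other provisions, and much of that reply stands.

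*Sponsor notice.* A reader might infer that some strokes reach the sponsor about three months late. The documents rule this out. C.5.2 requires all new or worsening adverse events to be captured through the 24-month visit and all strokes to be reported after that, and C.5.2.5 sets the 15-day limit. What changes after day 90 is the seriousness classification, not the sponsor's knowledge of the event.

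*The deadline.* A reader might also infer that the 3-day limit is impossible to meet. It is not. The clock is "not later than within 3 calendar days of first learning of any SAE", so a site that learns of disabling status at day 90 can still comply. The difficulty is that the category cannot be decided at onset.

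*The DSMB.* It would go too far to say that the DSMB cannot see these strokes for three months. C.5.4 lets it request other data and says that primary and safety-related secondary endpoints may be reviewed at full meetings. Stroke of any severity is part of MACCE and a secondary endpoint in its own right. The DSMB charter, which is not among the documents, may add more. These routes are discretionary on the face of the protocol, however, whereas the review of SAEs and deaths is a stated minimum.

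*Other checks.* C.5.3 has the Clinical Events Committee adjudicate adverse events related to the primary endpoint, and has sponsor safety staff check the classification of the rest. Neither can settle disabling status under O.2 before the 90-day score exists, so these checks do not close the gap.

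Finally, one may say that making all strokes serious is a preference. That is partly so. The protocol could instead state how a stroke is to be classed provisionally. At present it does neither.

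**Conclusion.** The point holds in a limited form. For a stroke that meets no standard SAE criterion, default seriousness cannot be settled until the 90-day mRS. The consequence is sponsor notice up to 12 days later and, if the stroke proves disabling, possible absence from the DSMB's minimum SAE listing until about day 93. Both figures assume that the site learns of the event at onset and that the 90-day score is taken on time.

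The number of subjects affected is not in the documents. A reader might try to derive one. C.6.5.2 expects about 2% disabling stroke at 24 months in 1600 subjects randomized 1:1, so 0.02 × 800 = 16 per arm. If 10% to 30% of these met no standard criterion at onset, that would be 1.6 to 4.8 per arm. Nothing in the documents supports that share, and the 16 covers all 24 months, including strokes after discharge that would often lead to admission. The figure is illustrative only. The group is probably small.

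The primary endpoint, its definition and its analysis are not touched. This is a cheap improvement to safety surveillance, not a flaw that threatens the trial's conclusions.

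**What to change.** Make two wording changes:

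1. In the added list in C.5.1.2, replace the stroke entry with: *All strokes (disabling status to be added after the 90-day mRS)*.
2. In O.2, Stroke and TIA, change the sentence that makes disabling strokes serious adverse events so that it covers all strokes in the same way.

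The definitions of disabling and non-disabling stroke, the primary endpoint and the secondary endpoints stay as they are. Seriousness can then be decided when the event is reported, and the 90-day score adds the severity class later.

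The cost is a small number of additional SAE reports for non-disabling strokes, many of which would already qualify through hospitalization.
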